### **Statistical Analysis:**

The IBM SPSS Statistics 22 (SPSS IBM, Turkey) program was used for statistical analysis. The normality of the parameters was assessed with the Shapiro-Wilk test. Mean, median, standard deviation, and frequency was used as descriptive statistical methods. The Student's t-test and ANOVA were used to make comparisons between the parameters in each group that showed normal distribution. The Mann-Whitney U and Kruskal Wallis test was used to make comparisons between the parameters in each group that lacked normal distribution. The data were assessed at  $p <0.05$  significance level and 95% confidence interval.

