## **The Effect of Vitamin D and Exercise on Balance in Postmenopausal Women- NCT03608488**

**(07/01/2019)**

### **Protocol:**

In this study postmenopausal women aged 50 to 70 years were included. Participants who had vitamin D3 level below 10ng/dl randomized to 3 groups as following:

Group I- Vitamin D replacement (50.000 IU/per week, for 8 weeks)

Group II- Core and balance exercises for 8 weeks.

Group III- Vitamin D replacement (50.000 IU/per week, for 8 weeks) plus core and balance exercises

Participants with vitamin D3 level above 30ng/ml were designed as control group (group IV). Core and balance exercises were given them as well for 8 weeks.

Evaluations were performed at baseline and 8 weeks after treatment.

Berg balance scale, postural stability tests, fall risk assessments and Nottingham Health Profile were used.

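### A Shapiro-Wilk result on the observed data decides between mean-based and rank-based tests, with no rule for outcomes on which the groups disagree

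*Combined protocol and SAP*

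**What the plan says.** The Statistical Analysis section has three sentences on the choice of test.

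- The screen: "The normality of the parameters was assessed with the Shapiro-Wilk test".
- The parametric branch: "The Student's t-test and ANOVA were used to make comparisons between the parameters in each group that showed normal distribution".
- The rank branch: "The Mann-Whitney U and Kruskal Wallis test was used to make comparisons between the parameters in each group that lacked normal distribution".

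The 0.05 level is attached to the data in general ("significance level and 95% confidence interval"). The section does not say whether that level also governs the Shapiro-Wilk test. It does not say whether baseline, 8-week or change values are screened, or whether the screen is run per group, on pooled data or on residuals. It gives no rule for mixed results and fixes no test in advance for any outcome.

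The Protocol section sets how often the screen is used. Participants with low vitamin D3 are "randomized to 3 groups as following". A fourth group, with vitamin D3 above 30 ng/ml, is not randomised. Four instruments are listed ("Berg balance scale, postural stability tests, fall risk assessments and Nottingham Health Profile were used"), and there are two visits ("Evaluations were performed at baseline and 8 weeks after treatment"). No sample size or expected distribution is given.

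**The concern.** A comparison across groups needs one test per outcome, so it needs one verdict on normality per outcome. If the screen is applied group by group it returns three or four verdicts. When they differ, the text points to both branches at once and the analyst must decide after seeing the data.

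The branches also answer different questions. The t-test and ANOVA compare means; Mann-Whitney and Kruskal-Wallis compare rank distributions. One instrument could be judged on means at baseline and on ranks at 8 weeks, or two instruments on different scales at the same visit. The results would then not be comparable in any simple way, and a reader could not tell whether the reported test was the planned one.

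**Working it through.** The plan states no sample size, power or error rate, so there is no figure of its own to reproduce.

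**Inputs from the documents.** Three randomised groups, four groups in all, four instruments, two visits, significance level 0.05.

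**Assumptions, not in the documents.** Shapiro-Wilk is run in each group at 0.05; groups are of equal size and independent; sample sizes and distributions are as stated below.

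**Step 1. Chance of conflicting verdicts, exactly normal data.** With per-group rejection probability p and k groups, verdicts conflict unless all pass or all fail: 1 - (1-p)^k - p^k.

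- k = 3, p = 0.05: 1 - 0.95^3 - 0.05^3 = 0.1425.
- k = 4, p = 0.05: 1 - 0.95^4 - 0.05^4 = 0.1855.

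If the four instruments are treated as independent, the chance of at least one conflict at one visit is 1 - (1-0.1425)^4 = 0.46 for three groups and 1 - (1-0.1855)^4 = 0.56 for four. Correlated instruments would alter these two figures.

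**Step 2. Conflict when data are not normal.** The rejection rate p was simulated (6,000 samples per setting, 10 to 50 per group) and put into the same formula.

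| Assumed distribution | 3 groups | 4 groups |
|---|---|---|
| Skewness 0.5 | 18-52% | 23-63% |
| Skewness 1.0 | 36-74% | 45-87% |
| Integer score capped at 56, underlying mean 51, SD 4 | 26-68% | 34-80% |
| Same cap, underlying mean 54, SD 3 | 73% at n=10, 9% at n=30, about 0 at n=50 | 85% at n=10, 12% at n=30, about 0 at n=50 |

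The last row marks the limit. Where non-normality is strong enough, or groups large enough, every group rejects and the conflict disappears.

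**Step 3. When the open choice alters the conclusion.** This requires two things in the same trial: the verdicts conflict, and ANOVA and Kruskal-Wallis fall on opposite sides of 0.05. It was simulated with 20 per group, one group shifted by 0.7 SD, normal, gamma(4) and gamma(2) data, and 5,000 replicates.

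| | Normal | Skewness 1.0 | Skewness 1.41 |
|---|---|---|---|
| 3 groups | 1.4% | 8.8% | 12.5% |
| 4 groups | 1.5% | 10.3% | 14.3% |

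Repeat runs move these by about a percentage point, so I summarise them as about 1.5% for normal data and 8-15% for skewness 1.0-1.4.

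**Step 4. Type I error.** Under no difference (three groups, 15 to 30 per group; normal, skewed and capped data; 4,000 replicates, nominal 5%):

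- ANOVA alone: 4.3-5.3%.
- Kruskal-Wallis alone: 4.3-5.1%.
- Fixed rule, ranks if any group rejects: 4.4-5.9%.
- Always taking the smaller p-value: 5.1-6.9%.

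**The case against.** The strongest reply is that this is a wording gap with little consequence. Part of it stands.

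- **Per-group testing is inferred.** The reference to each group sits in the two sentences on comparison tests, not in the Shapiro-Wilk sentence. A pooled or residual screen gives one verdict per outcome, and steps 1 to 3 would not apply. This stands as a limit on the figures. The observed data would still choose the test.
- **Error inflation is small.** This stands. A conventional tie-break keeps type I error near 5-6%. A reader might infer serious inflation, or that the smaller p-value was picked. The documents support neither: the first does not follow from step 4, and nothing in the text suggests the second.
- **Disagreement between two valid tests is not an error.** This also stands. A reader might take the overall rate at which ANOVA and Kruskal-Wallis differ (about 8%, 12% and 18% for normal data and skewness 1.0 and 1.4, four groups of 20) as the size of the problem. That counts trials in which the verdicts agreed and the rule gave an answer. The joint rate in step 3 is the relevant one, and for normal data it is about a fifth as large.
- **Raw scores against residuals.** It is tempting to add that the plan screens raw scores when the residuals are what matter. In a one-way comparison, a group's residuals are its scores minus its own mean, and Shapiro-Wilk is unaffected by that shift. Under the per-group reading the criticism fails. It would apply only to pooled raw scores, where the conflict argument falls away.
- **The text is in the past tense.** An unwritten rule may have existed. The documents cannot show this either way.

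**Conclusion.** The point holds in a limited form and should be corrected, though it does not by itself undermine the trial. The text certainly makes the choice of test depend on the observed data and gives no rule for mixed verdicts. The sizes are conditional on per-group testing at 0.05 and on assumed sample sizes and distributions. On those terms, conflict affects 14% to 18.5% of outcomes with exactly normal data and more in most of the skewed settings tried. The unresolved choice would change significance in about 1.5% to 15% of trials per outcome. Type I error reaches about 7% at worst. The harm lies in an unfixed analysis that can mix means and ranks across outcomes and visits, rather than in a large loss of error control.

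**What to change.** Remove the normality screen as a means of choosing the test, and name one analysis for every outcome: a linear model of the 8-week score on group (I, II, III) and baseline score, with heteroscedasticity-robust or permutation p-values. Keep residual plots as a diagnostic only. Report one rank-based sensitivity analysis for all outcomes, whatever any normality test shows. Group IV was formed by vitamin D level and not by randomisation, so report any comparison with it separately and label it non-randomised.

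Pre-specifying a rank-based analysis throughout would also remove the screen. The linear model is preferred because it uses the baseline score already collected and keeps every outcome on the scale of means.

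The cost is a few lines of SAP text and a little programming. The real downside is power under strong skew. In the step 3 set-up with four groups and skewness 1.41, unadjusted ANOVA had about 60% power and Kruskal-Wallis about 74%; with normal data the figures were about 59% and 56%. The sensitivity analysis would show whether this matters.

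If the analysis has already been done, state the rule that was used, including the unit of testing, the Shapiro-Wilk level and the handling of mixed verdicts, and report both the mean-based and the rank-based analysis for every outcome.

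### The named tests use only women with an 8-week value, with no as-randomised rule or paired test, so balance-related loss that differs by arm would bias the exercise comparisons

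*Combined protocol and SAP*

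**What the plan says.** The Protocol section sets out three randomised arms ("Participants who had vitamin D3 level below 10ng/dl randomized to 3 groups as following"). Group I receives vitamin D alone. The other two exercise: "Group II- Core and balance exercises for 8 weeks" and "Group III- Vitamin D replacement (50.000 IU/per week, for 8 weeks) plus core and balance exercises". Group IV also exercises, but it is defined by vitamin D level and is not randomised.

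Outcomes are measured twice: "Evaluations were performed at baseline and 8 weeks after treatment".

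The Statistical Analysis section names two families of test. For normally distributed measures, "The Student's t-test and ANOVA were used to make comparisons between the parameters in each group that showed normal distribution". For the rest, "The Mann-Whitney U and Kruskal Wallis test was used to make comparisons between the parameters in each group that lacked normal distribution". The criterion is "The data were assessed at $p <0.05$ significance level and 95% confidence interval".

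Neither section mentions an analysis population, analysis as randomised, women who stop treatment, missing 8-week values or a sensitivity analysis.

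**The concern.** With one post-baseline visit and no method for missing values, a woman without an 8-week value contributes nothing to any named test, whether it is applied to 8-week scores or to change. Applied as written, the plan analyses only women who have that value.

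This matters here because the arms ask different things of participants. Group I takes a weekly dose, while groups II and III follow an eight-week exercise programme. Several outcomes measure balance, which could itself influence whether a woman stays with balance exercise. If loss differs by arm and is related to balance, the groups compared at 8 weeks are no longer the groups formed by randomisation, and II versus I and III versus I are biased.

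A second, separate problem concerns change within a group. The wording allows comparisons within each group, which could mean baseline against 8 weeks. Neither a signed-rank test nor an explicitly paired test is named. If an unpaired test such as Mann-Whitney were used, the pairing would be ignored, and the baseline sample could include women missing from the 8-week sample. Loss of poor scorers alone could then appear as improvement.

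**Working it through.** **Inputs.** From the documents: one post-baseline visit, exercise in II and III but not in I, the named tests and the 0.05 level. The documents give no sample size, SD or drop-out rate, so there is no figure of the plan's own to reproduce. Everything below is illustrative. It assumes normal scores with SD 1 and no true treatment effect.

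**1. Shift in one arm.** Suppose the fraction d with the lowest value of a latent normal variable leaves, and that variable has correlation r with the 8-week score. The mean of those who remain rises by r × h(d), where h(d) = φ(z_d)/(1 − d).

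- h(0.10) = 0.195; h(0.20) = 0.350; h(0.30) = 0.497.
- 20% loss in the exercise arm only: 0.3 × 0.350 = 0.105; 0.5 × 0.350 = 0.175; 0.7 × 0.350 = 0.245 SD.
- r = 0.5 with 10% or 30% loss: 0.5 × 0.195 = 0.098; 0.5 × 0.497 = 0.249 SD.

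If good balancers leave instead, the sign reverses.

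**2. Loss in both arms.** The net bias is r × [h(d exercise) − h(d group I)]. It is zero when loss is equal with the same r in both arms, and zero when r = 0. With h(0.05) = φ(1.645)/0.95 = 0.103/0.95 = 0.109, loss of 20% against 5% at r = 0.6 gives 0.6 × (0.350 − 0.109) = 0.145 SD. Loss of 30% against 5% gives 0.6 × (0.497 − 0.109) = 0.233 SD.

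**3. Simulation check.** Two arms of 30, Student's t-test on women with an 8-week value, two-sided 5% level (sidedness is an assumption), 10,000 replicates per scenario:

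| Loss, exercise / no exercise | Bias at r = 0.3 (SD) | Bias at r = 0.6 (SD) | False positives at r = 0.6 |
|---|---|---|---|
| 10% / 10% or 20% / 20% | about 0 | about 0 | about 5% |
| 10% / 0% | 0.06 | 0.12 | 7.4% |
| 20% / 5% | 0.07 | 0.15 | 8.3% |
| 30% / 5% | 0.11 | 0.23 | 13.1% |

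For 30% / 5% at r = 0.6, false positives are 10.0% with 20 per arm and 19.7% with 50 per arm. With r = 0, every scenario stays near 5%.

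**4. Change scores.** If loss is tied to the 8-week score itself and the baseline to 8-week correlation is 0.6 (assumed), each shift is multiplied by 1 − 0.6 = 0.4. The range in step 1 becomes 0.105 × 0.4 = 0.042 to 0.245 × 0.4 = 0.098 SD. In the simulation with 30 per arm, unequal and balance-related loss gives a change-score bias of about 0.02 to 0.09 SD, with rejection of 5.1% to 6.2%.

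**5. Within-group change.** An unpaired comparison of all baseline values with the remaining women's 8-week values shows the full shift of step 1 as change: 0.105 to 0.245 SD at 20% loss. This needs no difference in loss between arms. Computing change per woman on those with both visits leaves only the step 4 amount, so pairing removes the changing-sample part but not the selection.

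**6. Sensitivity analysis.** Assigning leavers their baseline value changes the shift to r × φ(z_d) × (1 − 0.6). At 20% loss and r = 0.5 this is 0.5 × 0.280 × 0.4 = 0.056 SD, against 0.175 SD without it.

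**The case against.** The strongest reply is that the documents are silent on drop-out, and silence is not conduct. A reader might infer that women who stop are removed from follow-up or moved between groups. Nothing in either section says so; the plan simply does not provide for keeping them. That reply stands, and the point is limited to the omission.

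A reader might also infer that all four named tests are for independent samples. That goes too far. Mann-Whitney and Kruskal-Wallis are, but Student's t-test has a paired form and ANOVA a repeated-measures form, and the plan does not say which is meant. The false within-group change therefore depends on within-group testing being done, done unpaired, and done with all baselines kept. The wording permits this without establishing it.

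Third, the direction and size of any bias are assumed. No passage shows that poor balancers leave, that loss differs by arm, or that anyone left. Loss confined to the exercise arms is an extreme contrast, and 20% against 5% gives less. Analysing change, a natural use of the baseline visit, brings error rates close to nominal under the assumptions of step 4. The difference in burden also says little about III versus II, where both arms exercise, and comparisons with group IV are non-randomised however drop-out is handled.

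These replies limit the claim but do not remove it. Neither section supplies an as-randomised rule or a way to deal with missing 8-week values.

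**Conclusion.** The concern holds as a conditional one. As written, the analysis rests on women with an 8-week value, without provision for analysis as randomised and without a signed-rank or explicitly paired test for within-group change. II versus I and III versus I are biased if loss both differs by arm and is related to balance, in a direction set by who leaves. Under 20% loss in the exercise arms only and r of 0.3 to 0.7, the bias on raw 8-week scores is about 0.10 to 0.25 SD. It is smaller on change scores if loss follows the 8-week score, and near zero if loss is equal or unrelated to balance.

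The documents do not support the stronger conclusion that drop-out did make exercise look better. With no drop-out reported, the actual bias could be nil. The point should be corrected, but it does not by itself invalidate the trial.

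**What to change.** 1. State that every randomised woman with an 8-week value is analysed in the group to which she was randomised, whether or not she completed treatment. Where still possible, obtain the 8-week evaluation from women who stopped. The text is in the past tense, so this may come too late, and if it is feasible it is a follow-up procedure and not only wording.
2. Test any within-group change per woman, on those with both visits, with a paired t-test or Wilcoxon signed-rank test. Say that this remains a completers' analysis.
3. Report losses by arm with the leavers' baseline scores. Repeat the comparisons among I, II and III with leavers assigned their baseline value, as a sensitivity analysis only. State that this single imputation assumes no gain and understates uncertainty.

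The cost is a few sentences in the Statistical Analysis section, a table of losses and one extra run in SPSS. As-randomised effects may be slightly smaller than effects among completers. Analysis as randomised and items 2 and 3 can be done on data already collected.

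### Pooled-variance Student's t and ANOVA are named after a normality check only, although nothing in the design ties the spread or size of the non-randomised group IV to the randomised groups

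*Combined protocol and SAP*

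**What the plan says.** The Statistical Analysis section states: "The normality of the parameters was assessed with the Shapiro-Wilk test". For parameters that pass, Student's "t-test and ANOVA were used to make comparisons between the parameters in each group that showed normal distribution"; the rest go to Mann-Whitney U and Kruskal-Wallis. Results are judged at p<0.05, with a "significance level and 95% confidence interval". The section mentions no check of equal variances, no unequal-variance version of either test and no robust standard error. It does not list which pairs of groups are compared, or which outcomes took which route.

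The Protocol section randomises only women with low vitamin D3, to groups I, II and III. Group IV is formed differently: "Participants with vitamin D3 level above 30ng/ml were designed as control group (group IV"). These women did the same kind of exercise programme as group II. Neither section gives a group size, an allocation ratio or a standard deviation.

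**The concern.** Student's t and one-way ANOVA, as named, assume a common variance as well as normality. Among groups I to III, randomisation makes similar spread at baseline a reasonable expectation. Group IV has no such protection: it is selected on a different vitamin D3 level, and no stated ratio fixes its size.

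If both the size and the spread of group IV differ from those of the comparison group, the pooled standard error is wrong. It is too small when the smaller group has the larger SD, and too large when the larger group does. A comparison of group II with group IV, or a four-group ANOVA, could then be too liberal or too conservative while still being reported at 5% with a 95% interval.

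**Working it through.** **Inputs.** From the documents: a 5% level (taken as two-sided, since a 95% interval is named), pooled tests, three randomised groups and one non-randomised group. Assumed, because the documents are silent: 20 women in each randomised group with SD 1, group IV with n4 women and SD s, normal data and equal true means.

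**Step 1: the plan's own figure.** With equal SDs the 5% level is exact in theory. In simulations with 15 to 30 women per randomised group and group IV at half, equal or twice that size, Student's t rejected 4.9 to 5.1% and ANOVA 4.9 to 5.1%. So unequal size alone does no harm.

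**Step 2: the standard error.** For one randomised group against group IV:

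- true variance of the difference: V = 1/20 + s²/n4
- variance that the pooled test expects: P = [(19 + (n4 − 1)s²)/(18 + n4)] × (1/20 + 1/n4)

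With n4 = 40 and s = 0.5: V = 0.05 + 0.25/40 = 0.0563, and P = (28.75/58) × 0.075 = 0.0372. V/P = 1.51, so the true standard error is √1.51 = 1.23 times the one used.

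With n4 = 10 and s = 0.5: V = 0.05 + 0.25/10 = 0.0750, and P = (21.25/28) × 0.15 = 0.1138. V/P = 0.66, so the true standard error is 0.81 times the one used.

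With n4 = 20, V = P for any s, which is why equal sizes protect the t-test.

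**Step 3: rejection rates under no true difference** (simulation, at least 200,000 replicates per scenario):

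| n4 | SD ratio s | V/P | Student's t | Welch's t |
|---|---|---|---|---|
| 20 | 0.5 | 1.00 | 5.2% | 5.0% |
| 25 | 0.8 | 1.05 | 5.6 to 5.7% | 5.0% |
| 16 | 0.8 | 0.95 | 4.5% | 4.9% |
| 40 | 0.67 | 1.30 | 8.5% | 5.0% |
| 40 | 0.5 | 1.51 | 11.1% | 5.0% |
| 10 | 0.5 | 0.66 | 1.9% | 4.9% |
| 10 | 2 | 1.53 | about 11.5% | 5.1 to 5.2% |

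Four-group ANOVA with 20 women in each of groups I to III: 9.7% (n4 = 40, s = 0.5), 8.0% (n4 = 40, s = 0.67), 3.8% (n4 = 10, s = 0.5), 5.6% (n4 = 20, s = 0.5) and 6.7% (n4 = 20, s = 2). Welch's ANOVA gave 5.0 to 5.1% in these five settings. Results changed little between 15 and 30 women per randomised group.

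**Step 4: power cost of Welch's t when variances are in fact equal** (d = true difference divided by the common SD):

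- 20 vs 20, d = 0.6: 45.5% falls to 45.4%, about 0.1 point
- 20 vs 40, d = 0.6: 57.8% falls to 57.0%, about 0.8 point
- 20 vs 10, d = 0.6: 32.2% falls to 31.1%, about 1.1 points
- 20 vs 10, d = 1.0: 70.3% falls to 68.3%, 2.0 points

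**The case against.** The strongest reply is that both ingredients of the harm are hypothetical. A material error needs unequal sizes and unequal spread together, and the documents report neither. The 11% figure needs a two-fold size imbalance and a four-fold variance ratio; mild departures move the t-test by half a point or so. This stands, and it limits the point to a conditional one. It does not remove it: robustness of the pooled tests depends mainly on near-equal sizes, and the documents do not promise those either.

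A reader might infer that group IV was recruited separately. The Protocol section does not say so. It gives one entry population, postmenopausal women aged 50 to 70, and assigns group IV by vitamin D3 level. The argument needs only that group IV is non-randomised and differently selected, which the text does show.

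It is also fair to object that a II versus IV t-test is inferred, since no pairs are listed, and that Welch's tests mend only part of the plan. Mann-Whitney U responds to the same imbalance: with 20 vs 40 women and half the SD it rejects 8.8%, and with 20 vs 10 women and half the SD 3.0%. Both objections stand, and they define the scope of the fix.

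**Conclusion.** The point holds as a cheap improvement, not as a demonstrated error. The plan relies on equal variances without checking them, in a design where one of the four groups has no randomisation to support that assumption. Under the assumed settings the true level of a nominal 5% t-test against group IV runs from about 2% to between 11 and 12%. It stays between 4.5% and 5.7% when sizes are equal or the departures are mild.

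Three stronger readings are not supported. The documents do not show that variances or sizes differ, so it cannot be said that the reported p-values are wrong, or in which direction. The concern does not extend to comparisons among randomised groups of similar size. And a correct standard error would not make the group IV comparison causal: group IV differs by vitamin D status, and that confounding is a separate matter.

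**What to change.** For normally distributed parameters, specify Welch's t-test and Welch's ANOVA (or a regression model with heteroscedasticity-robust standard errors) for every comparison that includes group IV, and report the confidence intervals that go with them. State the size and SD of each group beside the results, so that a reader can see whether the choice mattered.

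The change needs no new data. Its price is the power loss in Step 4, paid only if variances are in fact equal. The section is written in the past tense, so analyses already done would have to be rerun; that would also show whether any conclusion changes. Non-normal parameters stay on the rank tests, and the plan should say that this route has the same sensitivity to unequal spread and size.
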